4.3 End of Study Definition

A participant is considered to have completed the study if the parents or LARs have completed the last contact planned in the SoA (telephone contact at D366 for France, Germany, and UK non-reconsented participants and telephone contact at D731 for UK reconsented participants).

The end of the study is defined as the date of the last contact of the last participant in the study.

However, for periodic safety reports, the study is considered completed when the clinical study report is finalized.

5 Study Population

Prospective approval of protocol deviations to recruitment and enrollment criteria, also known as protocol waivers or exemptions, is not permitted.

5.1 Inclusion Criteria

Participants are eligible for the study only if all of the following criteria are met:

Age

I01: Born at \geq 29 weeks gestational age and aged 0 to 12 months (calendar age), who are entering their first RSV season on the day of randomization in the study (D01)^a

Informed Consent

102: Informed consent form has been signed and dated by the parent(s) or other LAR(s) (and by an independent witness if required by local regulations)

Other

103: Participant and parent/LAR are able to attend the scheduled visit and to comply with all study procedures^b.

5.2 Exclusion Criteria

Participants are not eligible for the study if any of the following criteria are met:

Medical conditions

- **E01:** Known or suspected congenital or acquired immunodeficiency; or receipt of immunosuppressive therapy, such as anti-cancer chemotherapy or radiation therapy, within the preceding 6 months; or long-term systemic corticosteroid therapy (prednisone or equivalent for more than 2 consecutive weeks within the past 3 months)
- E02: Active confirmed RSV infection at the time of dosing/randomization
- **E03:** Active LRTI at the time of dosing/randomization
- **E04:** Known systemic hypersensitivity to any of the study intervention components, or history of a life-threatening reaction to the study intervention used in the study or to a product containing any of the same substances^c
- **E05:** Laboratory-confirmed thrombocytopenia, or known thrombocytopenia, as reported by the parent/LAR, contraindicating intramuscular injection
- **E06:** Bleeding disorder, or receipt of anticoagulants in the 3 weeks preceding inclusion, contraindicating intramuscular injection
- **E07:** Any condition that, in the opinion of the investigator, is at a stage where it might interfere with study conduct or completion

^a "0 to 12 months" means from the day of birth to the day before the 13th month after birth.

It is to be noted that "complying with all study procedures" includes the parents or LARs willingness to install the study's dedicated application on their smartphone.

The components of study intervention(s) are listed in Section 6.1 of the protocol and in the Investigator's Brochure (IB).

E08: Moderate or severe acute illness/infection (according to investigator judgment) or febrile illness (temperature ≥ 38.0°C [≥ 100.4°F]) on the day of study intervention administration. A prospective participant should not be included in the study until the condition has resolved or the febrile event has subsided

Prior/concomitant therapy

- **E09:** Mother of the infant participant was administered an RSV vaccine during her pregnancy with the infant participant
- E10: Receipt of any monoclonal antibody by the infant participant
- **E11:** Receipt of immune globulins, blood or blood-derived products in the past 3 months by the infant participant

Prior/concurrent clinical study experience

E12: Participation at the time of study enrollment or planned participation during the present study period in another clinical study investigating a vaccine, drug, medical device, or medical procedure^a

Other exclusions

- E13: Eligible to receive palivizumab at time of inclusion (as per local guidelines)
- E14: In an emergency setting or hospitalized involuntarily
- **E15:** Identified as a natural or adopted child of the Investigator or employee with direct involvement in the proposed study

5.3 Lifestyle Considerations

No restrictions other than the ones listed in the exclusion criteria are required.

5.4 Screen Failures

Screen failures are defined as participants whose parents or LARs consent to participate in the clinical study but are not subsequently randomly assigned to study intervention/no intervention. Screening information is recorded in the source documents.

Individuals who do not meet the criteria for participation in this study (screen failure) can be rescreened.

^a It is to be noted that strictly observational studies do not fall under this exclusion criterion.

^b An infant in an emergency setting could include one who may be with next of kin or emergency services in case the parents are hospitalized, in jail, or dead. Involuntary hospitalization of an infant could be due to a court order or mediated by social services, without the consent of the parents.

6 Study Intervention and Concomitant Therapy

Study intervention is defined as any investigational intervention(s), marketed product(s), placebo, or medical device(s) intended to be administered to a study participant according to the study protocol.

Note: Concomitant therapies such as vaccines or products administered outside of study protocol are not considered as study interventions and are reported in the eCRF as reportable medications (see Section 6.8).

6.1 Study Intervention Administered

Study interventions are described in Table 6.1.

Table 6.1: Identity of study intervention

Intervention Name	Nirsevimab	
Use	Experimental	
IMP and NIMP	IMP	
Туре	Extended half-life monoclonal antibody	
Dose Form	Sterile solution for injection	
Unit Dose Strength(s)	100 mg/mL	
Excipients/Diluent	 30 mM histidine/histidine-HCl 80 mM arginine-HCl 120 mM sucrose 0.02% (w/v) polysorbate 80 pH 6.0 water for injection 	
Dosage Levels	0.5 mL presentation corresponding to 50 mg (if weight < 5 kg) or 1.0 mL presentation corresponding to 100 mg (if weight \geq 5 kg) at D01	
Number of Doses / Dosing Interval	1 dose	
Route of Administration	IM	
Site of Administration	Anterolateral aspect of the thigh according to standard practice procedures for IM injections in infants	
Injection Site Side	Either	
Sourcing	Provided by AstraZeneca	
Packaging and Labeling	AstraZeneca	
Current/Former Name or Alias	n/a	

Batch Number	TBD
Storage Conditions	The IMP will be stored in a refrigerator at a temperature ranging from +2°C to +8°C. The IMP must not be frozen, shaken, or exposed to light. Keep the prefilled syringe in the outer carton in order to protect from light.

Abbreviations: IM, intramuscular; IMP, Investigational Medicinal Product; n/a, not applicable; NIMP, Non-Investigational Medicinal Product; TBD, to be determined

The participant's weight at enrollment will determine the dose of nirsevimab to be administered. The dose of nirsevimab will be 50 mg for participants weighting < 5 kg and 100 mg for participants ≥ 5 kg at D01.

Study arms and associated study intervention are summarized in Table 6.2.

Table 6.2: Arms and Associated Study Interventions

Arm name	Group 1	Group 2
Associated study interventions	Nirsevimab	No intervention

6.2 Preparation/Handling/Storage/Accountability

Detailed guidance and information are provided in the investigator site file/regulatory binder.

- 1) The investigator or designee must confirm appropriate temperature conditions have been maintained during transit for all study intervention received and any discrepancies are reported and resolved before use of the study intervention.
- 2) Only participants enrolled in the study may receive study intervention and only authorized site staff may supply or administer study intervention. All study intervention must be stored in a secure, environmentally controlled, and monitored (manual or automated) area in accordance with the labeled storage conditions with access limited to the investigator and authorized site staff.
- 3) The investigator, institution, or the head of the medical institution (where applicable) is responsible for study intervention accountability, reconciliation, and record maintenance (ie, receipt, reconciliation, and final disposition records).
- 4) Further guidance and information for the final disposition of unused study interventions are provided in the IMP operating manual.

6.3 Measures to Minimize Bias: Randomization and Blinding

6.3.1 Randomization and Allocation Procedures

On the day of randomization, participants who meet all the inclusion criteria but none of the exclusion criteria with a signed informed consent from the parent(s) or other LAR will be

randomly assigned to Group 1 (nirsevimab) or Group 2 (no intervention) in a 1:1 ratio, stratified according to country and age at the time of randomization (ie, age \leq 3.0 months, age > 3.0 to \leq 6.0 months, and age > 6.0 months).

Site staff will connect to the IRT, enter the identification and security information, and confirm a minimal amount of data in response to IRT prompts. The IRT will then provide the subject randomization number and the group assignment and have the site staff confirm it. The full detailed procedures for group allocation are described in the IRT user guidelines. If the participant is not eligible to participate in the study, then the information will only be recorded on the participant recruitment log. If the parents or LARs of a participant have signed the consent but the participant is not randomized, the participant number and the reason of the screening failure will be recorded in the IRT database and then transferred in the clinical database.

Participant randomization numbers that are assigned by the IRT will consist of a 12-digit string (a 3-digit country identifier, a 4-digit study center identifier, and a 5-digit participant identifier). For example, Participant 250000100005 is the fifth participant enrolled in Center Number 1 in France (250 being the France country code). Participant numbers should not be reassigned for any reason.

The randomization codes will be kept securely in the IRT.

6.3.2 Blinding and Code-breaking Procedures

Code-breaking procedures are not applicable as this is an open-label study.

Blinding remains a methodological safeguard in clinical trials and is important for limiting bias, such as selection bias, detection bias, and performance bias. In this open-label pragmatic study, nirsevimab immunization will be compared to standard-of-care, ie, no intervention, and having a blinded third party or clinician assessing the patient outcomes is not feasible. Whether the compared groups will receive similar amount of attention cannot be ensured and this, in turn, can result in biased treatment effect estimates with uncertainties on the direction of the bias (underascertainment/over-ascertainment). Methods that decrease risk of bias will be used, such as standardization of questionnaires, a narrowly-defined and objective primary outcome, and when possible electronic health records to retrieve the primary clinical endpoints. Response rates to the questionnaires between the 2 groups will inform about the risk of bias.

6.4 Study Intervention Compliance

The following measures will ensure that the study intervention is administered as planned (see Table 6.1), and that any non-compliance is documented so that it can be accounted for in the data analyses:

- Nirsevimab immunization will be performed by qualified and trained study personnel
- The person in charge of study intervention management at the site will maintain accountability records of study intervention delivery to the study site, study intervention inventory at the site, dose given to each participant, and unused or wasted doses

6.5 Dose Modification

Not applicable.

6.6 Continued Access to Study Intervention After the End of the Study

Not applicable.

6.7 Treatment of Overdose

Since the study intervention is administered by a health care professional, it is unlikely that overdose by injection occurs.

However, in the event of an overdose, the investigator or other site personnel should:

- 1) Contact the RMO immediately.
- 2) Closely monitor the participant for any AE/SAE.
- 3) Document the quantity of the excess of the overdose in the source documents.

6.8 Concomitant Therapy

The following concomitant reportable medications will be collected:

- Medications that may affect the interpretation of safety data (eg, an antipyretic or analgesic that could have reduced the intensity or frequency of an AE)
- All vaccines administered within 14 days before and after dosing/randomization. It is to be noted that routine childhood vaccines scheduled at the time of the enrollment visit should be administered as planned
- All medications administered within 14 days before and after admission for LRTI hospitalization
- Routine immunization with nirsevimab (Beyfortus). For countries where Beyfortus has been made commercially available during the study conduct, the sites will be asked to report any routine immunization with Beyfortus.

Reportable medications will be collected in the eCRF. Dosage, homeopathic medication, topical steroids, as well as topical, ophthalmic, and ear treatments will not be recorded (except topical analgesics applied at the injection site of study intervention). Inhaled steroids will be recorded only when prescribed during a wheezing episode (see below).

Medications given in response to an AE will be captured in the "Action Taken" section of the AE eCRF.

For UK reconsented participants, the following concomitant medications will be collected:

- Medications related to related SAE and/or LRTI hospitalization
- Any medications prescribed during a wheezing episode.

Medications will be coded using the WHODrug dictionary.

6.8.1 Rescue Medicine

Appropriate medical equipment and emergency medications, including epinephrine (1:1000), must be available at the study site in the event of an anaphylactic or other immediate allergic reaction.

7 Discontinuation of Study Intervention and Participant Discontinuation/Withdrawal

7.1 Discontinuation of Study Intervention

Not applicable as there is only one immunization visit.

7.2 Participant Discontinuation/Withdrawal from the Study

- A participant may be withdrawn from the study at any time at her/his parents or LARs request or may be withdrawn at any time at the discretion of the investigator for safety, behavioral, or compliance reasons. This is expected to be uncommon.
- The reason for withdrawal should be clearly documented in the source documents and in the eCRF: Adverse Event, Lost to Follow-up, Protocol Deviation, or Withdrawal by Parents or LARs.
- For participants hospitalized due to a LRTI symptoms who are withdrawn from the study, the Investigator or designee may seek information from the facility where medical attention was sought to complete the participant's eCRF and assess the case. This retrospective collection of information on LRTI hospitalization for participants withdrawn from the study will be possible only if the parents or LARs provided consent by ticking the corresponding box in the informed consent form.
- The participant will be permanently discontinued from the study at that time.
- If the parents or LARs of the participant withdraw consent for disclosure of future information, the Sponsor may retain and continue to use any data collected before such a withdrawal of consent.
- Withdrawn participants will not be replaced.

Follow-up of Discontinuations

For participants who have prematurely terminated the study, the site should attempt to contact their parents or LARs and complete all scheduled safety follow-ups, except if they specified that they do not want to be contacted again and it is documented in the source document.

For participants where the reason for early termination is lost to follow-up, the site will not attempt to obtain further safety information after last contact attempt on the 12-month follow-up for France, Germany, and UK non-reconsented participants and on the 24-month follow-up for UK reconsented participants. See Section 7.3 for definition of "lost to follow-up".

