9.4.2 Primary Endpoint

The primary endpoint is the overall incidence of RSV LRTI hospitalization through the RSV season in healthy term and preterm infants in all 3 countries combined. The determination of RSV LRTI hospitalization is based on the criteria described in Section 8.1.2.2.

The efficacy of nirsevimab in preventing RSV LRTI hospitalization compared to no intervention will be estimated accounting for the follow-up time post-dosing/randomization up to the data cut-off date for the Primary Analysis as follows:

 $(1-(CN/NN)/(CC/NC)) \times 100\%$

where:

- CN and CC are the numbers of RSV LRTI hospitalization through the RSV season in the nirsevimab and the control (ie, no intervention) groups, respectively.
- NN and NC are the total person-time contributed by participants randomized in the nirsevimab and the control groups, respectively.

The 95% CI for the efficacy will be calculated by an exact method assuming a binomial distribution of the number of RSV LRTI hospitalizations in the nirsevimab group conditional on the total number in both groups accounting for the follow-up time post-dosing/randomization.

The superior efficacy of nirsevimab in preventing RSV LRTI hospitalization will be concluded if the lower bound of the efficacy is > 0%. The primary efficacy analysis of the primary endpoint will be performed on all randomized participants.

If a participant experiences multiple occurrences of the same primary endpoint, only the first episode will be considered. The following rules will be applied in the calculation of the total person-time for the follow-up time:

- The start date for the follow-up will be the date of randomization for participants who are randomized to no intervention and the date of dosing for participants who are randomized to nirsevimab.
- For the participants who do not have the primary endpoint at the time of the Primary Analysis, the end date for the efficacy follow-up will be the end of the RSV season, or the last available date with confirmation of no RSV LRTI hospitalization for the Primary Analysis whichever is earlier. The efficacy follow-up will be censored at the end date.
- For the participants who have the primary endpoint at the time of the Primary Analysis, the end date for the efficacy follow-up will be the date of hospital admission.

The above-described analysis on the primary endpoint will also be conducted on the PPAS.

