3.1.4. Handling of Intercurrent Events to Reflect the Clinical Question of Interest

The following intercurrent events are anticipated during the study:

- Participant ends study early and withdraws consent from further data collection
- Participant ends study early without withdrawing consent from further data collection
- Participant who received Beyfortus (nirsevimab) as a routine medication during the study

The following table describes how intercurrent events will be collected and handled within the analysis.

Table 2 Handling of Intercurrent Events for the Primary Estimand

Intercurrent event	Data collection and analysis
Participant ends study early and withdraws consent from further data collection	Participants who withdraw consent from further data collection will be analyzed by while on treatment strategy: only data collected before the occurrence of the intercurrent event will be included in the analysis. Participants will be censored at the earliest of: (i) last available date with no confirmation of RSV LRTI hospitalization, (ii) end of the RSV season or (iii) data cut-off date for the Primary Analysis (see section 6.7.8)
Participant ends study early without withdrawing consent from further data collection	Participants who end study early without withdrawing consent from further data collection will be analyzed with a treatment policy strategy: if RSV LRTI hospitalization occurs after cut-off date or end of the RSV season whichever is earlier, it will not be considered. Participants will be censored at the earliest of (i) last available date with no confirmation of RSV LRTI hospitalization, (ii) end of the RSV season or (iii) data cut-off date for the Primary Analysis
Participant who received Beyfortus (nirsevimab) as a routine medication during the study	Participants who received Beyfortus will be analyzed by while on treatment strategy: only data collected before the occurrence of the intercurrent event will be included in the analysis. Participants will be censored at the earliest of: (i) last available date with no confirmation of RSV LRTI hospitalization, (ii) end of the RSV season or (iii) data cut-off date for the Primary Analysis or (iv) start date of Beyfortus

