 - for the participants who had no contact for safety events at all throughout the efficacy follow-up period, the end date for the efficacy follow-up will be date of randomization for participants who are randomized to no intervention, the date of treatment dosing for participants who are randomized to nirsevimab and treated, and the date of randomization for participants who are randomized to nirsevimab but not treated.

The total person-time for the follow-up time of each participant will be calculated as:

Person-months = (the end date - the start date + 1)/30.4375.

NN (days), the total person-time contributed by participants randomized in the nirsevimab, will be the sum of person-months for all the participants in the nirsevimab group. And NC (days), the total person-time contributed by participants randomized in the no intervention group, will be the sum of person-months for all the participants in the no intervention group.

The 2-sided 95% CI for the efficacy will be calculated by an exact method assuming a binomial distribution of the number of RSV LRTI hospitalizations in the nirsevimab group conditional on the total number in both groups (described by Breslow and Day⁷) accounting for the follow-up time post-dosing/randomization.

The superior efficacy of nirsevimab in preventing RSV LRTI hospitalization is concluded if the lower bound of 2-sided 95% CI of the efficacy is $> 0\%$. P-value will also be provided. The primary efficacy analysis of the primary endpoint will be performed with the All Randomized Set.

RSV season is the period of increased RSV infection. For the purpose of efficacy analyses, the start of the RSV season will be defined on a country-by-country basis and will be based on country-specific epidemiological surveillance and the cut-off date (28Feb2023, except for site parent contact and medical call center contact, for which the date of database lock for Primary Analysis will be used) will be used as end dates.

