6.6.2.2. Tipping-Point Analysis

Due to the open-label nature of the study, an excess of withdrawals might be observed in the no intervention group and be translated into a biased estimator when assuming the non-informative censoring hypothesis.

In order to test this hypothesis, a tipping point analysis^{8,9,10} will be performed to assess the impact of imputating missing data under a various range of hypotheses.

1. In order to perform the tipping point analysis, data will be imputed for all participants with missing data, (ie who discontinued the study, or with a RSV test equals to missing or Not Done) from both groups, several scenarios will be evaluated:
 - a. Best case scenario: no RSV LRTI hospitalization among the missing data in nirsevimab group whereas all missing data in the no intervention group will be imputed as RSV LRTI hospitalization.
 - b. Worst case scenario: all missing data in nirsevimab group will be imputed as RSV LRTI hospitalization whereas no missing data in the no intervention group will be imputed as RSV LRTI hospitalization.
 - c. The number of RSV LRTI hospitalizations imputed in each arm will be incremented from 0% (complete case analysis with no RSV LRTI hospitalization imputed in any arm), by 10%, to the total number of missing data in each arm. Remaining participants with missing data (from 90% of total number of missing data to 0%) will be then imputed as having no RSV LRTI hospitalizations.
2. For each combination:
 - a. Person-months will be imputed in both treatment groups using the overall distribution of person-months in the respective group for non-missing participants. The following values will be considered and evaluated as different scenarios: minimum value, Q1, Q2, Q3 and maximum value.
 - b. Corresponding Incidence Rates will be imputed in each treatment arm.
 - c. For non aggregated rows, Efficacy for participants with missing data will be provided

$$\text{Eff}_{\text{miss}} = 100 \times \left(1 - \frac{\text{Incidence Rate Miss Nirsevimab}}{\text{Incidence Rate Miss No Intervention}} \right) = 100 \times \left(1 - \frac{\text{IRN}_{\text{Miss}}}{\text{IRC}_{\text{Miss}}} \right)$$

- d. For non aggregated rows, Overall Efficacy will also be computed with its 2-sided 95% Confidence Interval (described by Breslow and Day as for primary analysis) and corresponding p-value

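### For infants who leave or go silent without withdrawing data consent, later hospitalizations can be counted while event-free time stops, so unequal loss between arms would bias primary efficacy

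*Protocol*

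**What the plan says.** The estimator in Protocol 9.4.2 and SAP 6.6.1 is one minus a ratio of incidence rates, where "NN and NC are the total person-time contributed by participants randomized in the nirsevimab and the control groups, respectively".

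**Infants with an event.** Under Protocol 9.4.2, "the end date for the efficacy follow-up will be the date of hospital admission". Protocol 7.2 and a Schedule of Activities footnote allow record retrieval after withdrawal for infants who were hospitalized: "For participants hospitalized due to a LRTI symptoms who are withdrawn from the study, the Investigator or designee may seek information from the facility". This requires a ticked consent box. SAP Table 2 (3.1.4) applies a treatment-policy strategy to infants who end the study early without withdrawing data consent. It excludes only late events: "if RSV LRTI hospitalization occurs after cut-off date or end of the RSV season whichever is earlier, it will not be considered".

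**Infants without an event.** Time ends at season end or "the last available date with confirmation of no RSV LRTI hospitalization for the Primary Analysis whichever is earlier"; the SAP adds the cut-off date. SAP 6.6.1 has a further rule, "for the participants who had no contact for safety events at all throughout the efficacy follow-up period, the end date for the efficacy follow-up" being set to the start date. With the SAP's person-time formula (end minus start plus 1), that is one day.

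**Withdrawal of data consent.** Table 2 uses only data collected before the withdrawal, so events and time are cut together.

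**Wording.** SAP Tables 2 to 4 give the censoring date as the "last available date with no confirmation of RSV LRTI hospitalization". Protocol 9.4.2, SAP 5.2.1 and the rest of SAP 6.6.1 use the opposite order, confirmation of no event.

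**The concern.** Whether an infant's later follow-up enters the analysis can depend on the outcome. A leaver or silent infant whose admission comes to light contributes an event and the time up to admission. The same infant without an admission contributes time only to the last confirmation.

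An event can surface without parent contact. The study card asks hospitals to identify the study site, the investigator may be the attending physician, and efficacy data are taken from medical records. The open-label investigator has discretion over whether to seek the record.

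Each arm's rate is inflated according to the time it loses. The inflation cancels in the ratio if loss and capture are alike. It does not cancel if, in the SAP's words (6.6.2.2), "an excess of withdrawals might be observed in the no intervention group". The same follow-up rule feeds the very severe RSV LRTI and country-level tests.

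**Working it through.** **1. The plan's own figures.** Protocol 9.2 assumes 1.1% control incidence and 60% efficacy. With 9,620 infants per country, 4,810 per arm: 4,810 × (0.011 + 0.0044) = 74.1 events, matching the stated 74. The two-proportion formula without continuity correction, at two-sided α 1.66% and 90% power, gives 4,741 per arm (9,482), within 3% of 9,620. The sizing reproduces. It offers no loss rate to use here; Protocol 7.2 says only that withdrawal should be uncommon.

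**2. The rules side by side.**

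| Infant | Later event | Later event-free time |
|---|---|---|
| Withdraws data consent | not counted | not counted |
| Ends study early, keeps data consent | counted if found and box ticked | stops at last confirmation |
| Silent, not formally discontinued | counted if found | stops at last confirmation |
| Never contacted | counted if found | one day |

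The first row is symmetric. The other three are not.

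**3. Formula.** Let f be the share of an arm's at-risk time that falls after the last confirmed date, and c the share of events in that time that are found. With a constant event rate and non-informative loss, events are proportional to (1 − f) + c·f and time to (1 − f). The rate is multiplied by m = 1 + c·f/(1 − f), and the estimated rate ratio is the true ratio × m(nirsevimab)/m(control). Both f and c are assumptions.

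**4. Results at true efficacy 60%.** Suppose 3% of nirsevimab and 10% of control infants are lost with half their time unobserved, so f = 0.015 and 0.05.
- c = 0.25: m = 1.0038 and 1.0132; efficacy = 1 − 0.4 × 1.0038/1.0132 = 60.4%.
- c = 1: m = 1.0152 and 1.0526; efficacy = 61.4%.

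| Time lost, nirsevimab / control | c = 0.5 | c = 1 |
|---|---|---|
| 2% / 2% | 60.0% | 60.0% |
| 2% / 5% | 60.6% | 61.2% |
| 2% / 10% | 61.7% | 63.3% |
| 5% / 10% | 61.1% | 62.1% |
| 5% / 20% | 63.5% | 66.3% |
| 10% / 5% | 58.9% | 57.8% |

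A simulation (14,430 per arm, five-month season, uniform loss times, full capture) agrees. Losing 4% and 10% of infants gives 61.6%; losing 4% in both arms gives 59.9%.

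**5. False-positive rate.** With no true effect, full capture and a nominal one-sided 2.5%, the exact test rejects as follows. The 174 events are 14,430 × 0.0086 × 1.4 from Protocol 9.2.

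| Time lost, nirsevimab / control | 61 events | 174 events |
|---|---|---|
| 2% / 2% | 2.0% | 2.0% |
| 2% / 5% | 2.0% | 2.9% |
| 2% / 10% | 3.6% | 7.5% |

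**6. Do the planned analyses remove it?** The Poisson, Kaplan-Meier and Cox analyses reuse the follow-up rule of SAP 6.6.1, so they carry the same mismatch. The tipping-point analysis imputes outcomes and person-months, but only for infants who discontinued or lack an RSV test. Protocol 7.3 does not deem a silent infant lost before the 12-month call (24-month for UK reconsented infants). With first enrolment planned for September 2022, those calls come after the 30 April 2023 limit for the Primary Analysis. The Schedule of Activities, by contrast, gives unanswered monthly contacts as an example of premature termination. Whether silent infants are in the imputation set is therefore unclear.

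**7. What two added runs would show.** If every infant with data consent contributes full time, the rate ratio is multiplied by [1 − f(1 − c)] for nirsevimab over the same term for control. At 2% / 10% and c = 0.5: 0.99/0.95 = 1.0421, so efficacy = 1 − 0.4 × 1.0421 = 58.3%. The primary rule gives 61.7%. Cutting both events and time at last contact (c = 0) gives 60.0%. Under these assumptions the full-time run errs in the opposite direction to the primary rule, and the last-contact run lies between them.

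**The case against.** The strongest reply is that the exposure is small and partly managed.
- Case finding normally starts with a parent's report, so full capture among silent families is an upper bound.
- Sites must try to reach families after early termination, and missed monthly contacts trigger reminders and a call.
- SAP 6.6.1 uses database lock rather than 28 February 2023 for site and call-center contacts, and the Primary Analysis is rerun with late data.
- Time to discontinuation and eDiary response are also reported.
- At 61 events split 17 to 44 with equal person-time, the exact 95% interval is about 31% to 79%, far wider than the bias.

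All of this stands. It reduces lost time and capture but leaves the rule asymmetric.

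Stronger readings are tempting but unsupported. A reader might infer that all post-withdrawal events are counted; Table 2 excludes them when data consent is withdrawn. A reader might infer that the SAP forecasts more control withdrawals; it says only that they might occur, and Protocol 6.3.2 calls the direction of bias uncertain. A reader might infer that efficacy is therefore overstated; that needs both greater control loss and real capture of later cases.

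Cutting the primary analysis at the discontinuation date might also look like the obvious cure. It would replace the treatment-policy strategy, which is an estimand choice, and would miss silent infants, who have no such date.

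The reversed wording in Tables 2 to 4 is probably a word-order slip. But SAP 6.6.1 sends discontinued infants to Table 2, so it should be corrected.

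**Conclusion.** The asymmetry is in the text for infants who leave or go silent with data consent intact. Its effect on efficacy is conditional: upward if the control arm loses more observed time and later cases are found, nil if loss and capture are equal, and downward if the nirsevimab arm loses more. At true efficacy 60%, modest differential loss gives about 0.4 to 3 points, depending on capture; larger gaps such as 5% against 20% give more. These sizes rest on assumed loss and capture rates, a constant event rate, equal capture in both arms and non-informative loss. The documents do not show that the bias occurred. The point is worth acting on because the checks that would expose it are cheap and the planned analyses may miss silent infants.

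**What to change.** Keep the primary treatment-policy rule and make four changes to the SAP.

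1. Add a sensitivity run of the exact method in which every randomized infant who has not withdrawn data consent contributes time to the earliest of event, Beyfortus receipt, season end and cut-off, including infants never contacted.
2. Add a companion run that counts events and time only up to the last confirmed contact. Report both beside the primary estimate.
3. Put silent infants (no confirmed contact to season end or cut-off) into the tipping-point missing-data set, and state their status at the Primary Analysis.
4. In Tables 2 to 4, align the censoring date with Protocol 9.4.2, SAP 5.2.1 and SAP 6.6.1.

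The cost is SAP wording and a few runs of existing methods. SAP section 7 describes the Primary Analysis as already performed and rerun, so the added runs should be labelled post hoc. The full-time run assumes that unobserved infants had no undetected event; the companion run discards some real later events and assumes non-informative loss.
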